8.8.2 Clinical Laboratory Evaluations

Laboratory results (hematology and blood chemistry) will be summarized by treatment groups using descriptive statistics for observed and change from baseline values for all the post baseline assessments visits. The categorical parameters from urinalysis will be summarized by frequency counts and percentages.

Additionally, shift tables will be produced. The shift tables will be based on the classification of laboratory results i.e. Low/Normal/High of post baseline visits compared to the grading of baseline results.

A full subject listing will be presented for laboratory results.

Serum pregnancy test results for female subjects will be listed.

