6.3.2 Exclusion Criteria

Potential study subjects will be excluded if one of the following exclusion criteria is present:

1. The subject has a history of type 1 diabetes mellitus or a secondary form of diabetes.
2. The subject has received insulin within 1 year prior to the screening visit (Day –28), with the exception of insulin therapy during hospitalization or insulin therapy for medical conditions not requiring hospitalization (< 2 weeks' duration).
3. The subject has received an anti-diabetic drug (described in "6.5.1 Prohibited Concomitant Medications (1)Anti-diabetic drugs") within 8 weeks prior to the screening visit (Day –28).
4. The subject has a medical history of heart failure (New York Heart Association class III-IV), ventricular tachycardia or ventricular fibrillation.
5. The subject has a history of acute myocardial infarction, congestive heart failure or unstable angina within 6 months prior to the screening visit (Day –28).
6. The subject has any clinically significant electrocardiogram (ECG) abnormalities such as QTc prolongation of ≥ 500 ms at either or both of the screening visit (Day –28) and the randomization visit (Day 1).
7. The subject has a serious diabetic complication (proliferative retinopathy, Grade IV or more severe renal impairment or serious diabetic neuropathy).
8. The subject has a history of drug abuse.
9. The subject drinks on average more than 28 units of alcohol per week. (One unit of alcohol equals approximately 250 mL of beer, 125 mL of wine or 20 mL of spirits)

10. The subject is suffering from serious concurrent renal disease or has serum creatinine > 2.0 mg/dL at the screening visit (Day -28).
11. The subject has a clinically significant liver disease with aspartate aminotransferase (AST) or alanine aminotransferase (ALT) > 2.5 times the upper limit of normal at the screening visit (Day -28).
12. The subject is suffering from concurrent malignancy or has a history of malignancy, except those with no recurrent malignancy over the last 5 years.
13. The subject has systolic blood pressure > 180 mmHg or diastolic blood pressure > 100 mmHg at the screening visit (Day -28) or on Day -14.
14. The subject has participated in any other clinical study involving blood draws or administration of an unlicensed medicinal product within 3 months prior to the screening visit (Day -28).
15. The subject has donated blood within 3 months prior to the screening visit (Day -28).

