6.2.2 Windows

For the purpose of effectiveness and safety analysis, all scheduled and unscheduled clinic visits will be windowed as presented in the below table. The planned protocol visit window will be used for analysis.

Table 3 Schedule of Visits

Visit	Week	Scheduled Study Day	Visit Window in Protocol (Days)
Randomization Visit (RV)	Randomization Visit (RV)	1	1
Visit 1	Week 4	28	21 – 35
Visit 2	Week 8	56	49 – 63
Visit 3	Week 12	84	77 – 91
Visit 4	Week 16	112	105 – 119
Visit 5	Week 20	140	133 – 147
Visit 6	Week 24	168	161 – 175
Follow-up Visit	Week 26	182	182 – 196

If a visit day is outside of these windows, then it is considered as non-windowed, otherwise it is windowed. If a subject has more than one assessment occurring in the same visit window, the data from the visit closest to the scheduled study day will be used. If two visits have the same distance from the scheduled study day, the data of the visit after the scheduled study day will be used.

The unscheduled visits will be chronologically arranged between two scheduled visits. The unscheduled visits will be numbered sequentially with an increment of 0.1 to the visit number corresponding to scheduled visit preceding the unscheduled visit. For example, if two unscheduled visits occur between visit 1 (visit number is 10) and visit 2 (visit number is 20), then these unscheduled visits will be numbered 10.1, 10.2 in the order they occurred.

The assessments made in unscheduled visits will be considered in imputation of missing assessment using Last Observation Carry Forward (LOCF) method for Week 12 or Week 24.

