7 STATISTICAL METHODS

7.1 General Methodology

All analyses will be performed after the database is locked and access has been removed from the database and the study treatment codes are unblinded.

All statistical tests will be two-sided with a significance level of $\alpha=0.05$, unless specified otherwise and will be performed using SAS® Version 9.2 or higher.

Statistical tests will be supported by presenting estimates and 95% confidence intervals (CI) for the respective treatment effects and differences between the treatment groups. These estimates, confidence intervals and p-value will be based on the respective statistical models used for the analysis.

Data will be summarized using descriptive statistics (number of non-missing values [n], mean, standard deviation [SD], median, minimum, and maximum) for continuous variables and using frequency counts and percentage for discrete variables.

For the purpose of display, the summary results will be rounded as follows:

- Min and Max: same number of decimals as the raw data.
- Mean and Median: one more decimal place than the raw data.
- SD/Standard Error (SE): one more decimal places than the raw data.
- Percentages will be displayed with one decimal precision. A zero count will not have the associated percentage presented on the table (i.e. no 0%).
- All p-values will be displayed with a leading zero except when the value is 1. All p-values will be displayed to four decimal places. If a p-value is less than 0.0001, then the value will be displayed as '<0.0001'. If a p-value is 1, then the value will be displayed as 1.0000. If the p-value cannot be calculated for any reason, the value listed will be 'NA'.
- CI: one more decimal place than the raw data.

For categorical variables with missing values, a category documenting the frequency of missing values will be displayed in the summary tables.

Subject listings of all data from the CRFs as well as any derived variables will be presented. Safety listings of clinical laboratory, vital signs and ECG will be presented by planned visit.

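### The laboratory tables in SAP 8.8.2 use three categories and one value per visit window, so they do not show upward shifts from a High baseline and can lose an abnormal result to a repeat test

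*SAP*

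**What the plan says.** SAP 8.8.2 plans four displays:

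- For haematology and chemistry, "descriptive statistics for observed and change from baseline values for all the post baseline assessments visits". SAP 7.1 defines these as n, "mean, standard deviation [SD], median, minimum, and maximum".
- Shift tables with the classes "Low/Normal/High of post baseline visits compared to the grading of baseline results".
- For urine, "The categorical parameters from urinalysis will be summarized by frequency counts and percentages".
- A listing: "A full subject listing will be presented for laboratory results". SAP 7.1 adds: "Safety listings of clinical laboratory, vital signs and ECG will be presented by planned visit".

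SAP 6.2.2 applies visit windows to safety as well as efficacy, and to unscheduled as well as scheduled visits. If a window holds several assessments, "the data from the visit closest to the scheduled study day will be used", and a tie goes to the later visit. A visit day outside every window is classed as non-windowed. The one specific use that section names for unscheduled results is LOCF imputation.

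Protocol 6.3.2 sets the liver enzyme exclusion at AST or "alanine aminotransferase (ALT) > 2.5 times the upper limit of normal", and the creatinine exclusion above 2.0 mg/dL, both at screening. Protocol 6.6.2.4 counts a clinically significant laboratory abnormality as an adverse event, and SAP 8.8.1 tabulates treatment-emergent events.

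**The concern.** Laboratory measurements are a named safety endpoint (Protocol 6.9.1.6). A reader of the laboratory tables will want to know how many subjects per arm had a large change, whatever their starting value and whenever the sample was drawn. The tables described in the SAP text do not answer that, for two reasons.

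First, three categories cannot register worsening in a subject who is already High at baseline. Second, the one-value-per-window rule was written for by-visit summaries. Applied to safety data, it can discard an abnormal result in favour of a repeat, and it gives no visit to results drawn between windows. Early-termination samples are the most important of these, because some of those subjects stop for an adverse event.

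**Working it through.** The plan states no figure for this point. The check uses the shift definition, the windows in SAP Table 3 and the entry limits.

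**1. Windows.** The scheduled days are 28, 56, 84, 112, 140 and 168, each ± 7 days. That gives six windows of 15 days, which match Table 3.

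**2. Worsening from a High baseline.** Take illustrative ALT values, with 2.4 × ULN at baseline (eligible) and 3, 5 or 10 × ULN on treatment. All three are High to High, the same cell as no change. The rise does enter the change-from-baseline statistics, but diluted. One subject going from 2 to 8 × ULN, among 120 with a value at that visit, moves the arm mean by (8 − 2)/120 = 0.05 × ULN. The visit maximum shows that subject if the value is the one kept, but a maximum does not say how many subjects rose.

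The documents give no share of subjects who are High at baseline. Assuming 20–30%, 0.20 × 120 = 24 to 0.30 × 120 = 36 subjects per arm could show no upward shift.

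**3. Displacement by a repeat.** Let the abnormal sample fall *k* days before the scheduled day (*k* = 1 to 7) and a single repeat follow *r* days later. The repeat lies |*r* − *k*| days from the scheduled day. It is kept if |*r* − *k*| ≤ *k*, with equality being the tie that goes to the later visit. This means *k* ≥ *r*/2. The number of the 15 window days on which the abnormal value is replaced is therefore 8 − ⌈*r*/2⌉.

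| Gap *r* (days) | Days on which the repeat replaces it |
|---|---|
| 1 or 2 | 7 of 15 |
| 3 | 6 of 15 |
| 5 | 5 of 15 |
| 7 | 4 of 15 |
| 10 | 3 of 15 |
| 14 | 1 of 15 |

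If the abnormal sample is on or after the scheduled day, a later repeat is always further away and never replaces it. A repeat outside the window does not replace it either.

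Examples at Week 12 (Day 84, window 77–91):

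- Abnormal Day 79, repeat Day 84 (5 against 0 days away): Day 84 is kept.
- Abnormal Day 80, repeat Day 87 (4 against 3): Day 87 is kept.
- Abnormal Day 82, repeat Day 86 (2 against 2, a tie): Day 86 is kept.
- Abnormal Day 84, repeat Day 91 (0 against 7): Day 84 is kept.

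**4. Days in no window.** Days 2–175 are 174 days. The windows cover 6 × 15 = 90, which leaves 84. These are Days 2–20 (19 days) and the five 13-day gaps 36–48, 64–76, 92–104, 120–132 and 148–160: 19 + 5 × 13 = 84. An unscheduled or early-termination sample on such a day has no visit in the by-visit tables.

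The fractions in steps 3 and 4 count days. They are not probabilities that a result is lost, because scheduled visits are aimed at the windows.

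**The case against.** The strongest reply is that the tables are not the whole laboratory display. There is a full subject listing, and unscheduled visits keep their own numbers under SAP 6.2.2, so their records survive. Any clinically significant laboratory abnormality is an adverse event, is followed up, and enters the tables by term, severity and relationship regardless of windows. This stands as a partial safeguard. A listing, however, gives no count per arm, and because safety listings are by planned visit, the text leaves open whether unselected or non-windowed values appear. The adverse event route depends on the investigator's judgement, with no numeric limit stated. Where a diagnosis is clear, the diagnosis is recorded and not the laboratory value.

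Three stronger readings are tempting, and the documents do not support them:

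- *A large rise would be counted nowhere.* A subject who goes from Normal to above 3 × ULN is counted as Normal to High, unless the value is displaced or non-windowed. The table hides the size of that rise, but it does count the subject.
- *The window rule systematically removes abnormal values.* The rule ignores the result itself, and displacement needs the timing in step 3. Protocol 6.6.2.4 foresees additional tests for clinically significant abnormalities at Week 24 or early termination, but the documents do not say how often or why repeats are done.
- *No table in the plan counts subjects by multiples of ULN.* The SAP contents list table shells (section 12) and listing shells (section 13) that are not in the text available. Only the body text can be judged.

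It is also fair to say that nothing in the documents promises worst-value shifts, that the entry limits are screening criteria and not on-treatment thresholds, and that laboratory data are descriptive with no formal test.

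**Conclusion.** The concern holds as a limitation of the laboratory summary tables in the SAP text. It is not an internal contradiction and does not touch the primary efficacy conclusion. For subjects High at baseline, upward change appears only in the change-from-baseline statistics and the per-visit maximum. For results before the scheduled day, a same-window repeat can take their place, on 7 of 15 window days at a gap of 1–2 days, falling to 1 of 15 at 14 days. Unscheduled and early-termination results on 84 of 174 days have no visit in these tables.

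The window counts follow from SAP 6.2.2 as written, taking non-windowed to mean not assigned to any visit. The 24–36 subjects per arm rests on an assumed 20–30% High at baseline. The true share, and the number of repeats, are unknown from the documents. The change should be made because it is cheap and because the limits should be set before anyone sees data by arm.

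**What to change.** In SAP 6.2.2, limit the nearest-day rule for laboratory safety data to the by-visit descriptive statistics. In SAP 8.8.2:

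1. Add shift tables from baseline to the worst post-baseline value, highest and lowest separately, using all scheduled, unscheduled and early-termination results after the first double-blind dose.
2. Add counts per arm of subjects exceeding prespecified multiples of ULN for AST and ALT (alone and together with bilirubin) and a prespecified creatinine limit, split by baseline status. The sponsor should choose the cut-offs and fix them before unblinding.
3. State that the laboratory listings include unscheduled and non-windowed results.

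If the table shells already contain such displays, the body text need only be brought into line with them. The cost is SAP wording and a few extra tables. No new data are needed and no clinical rule changes.

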8.8.3 Vital Signs

Vital signs (pulse rate, systolic and diastolic blood pressure, and body temperature) will be summarized by treatment groups using descriptive statistics for observed and change from baseline values for all the post baseline assessments visits.

A full subject listing will be presented for vital signs results.

8.8.4 Electrocardiogram (ECG)

ECG measurements (PR-interval (ms), RR-interval (ms), QRS-interval (ms), QT-interval (ms), QTc (ms) and heart rate (beats/min)) will be summarized by treatment groups using descriptive statistics for observed and change from baseline values for all the post baseline assessments visits.

The investigator interpretation of ECG results (normal, abnormal not clinically significant and abnormal clinically significant) will be summarized by treatment groups using frequency counts and percentages.

A full subject listing will be presented for the ECG result and investigator interpretation.

8.8.5 Physical Findings

A full subject listing will be presented for the physical examination screening result.

9 COMPUTER SOFTWARE

All analyses will be performed by [REDACTED] using version 9.2 or later of SAS® software. All summary tables and data listings will be prepared by utilizing SAS® software. The standard operating procedures (SOPs) of [REDACTED] will be followed in the creation and quality control of all data displays and analyses.

11 APPENDICES

11.1 APPENDIX 1: STATISTICAL ANALYSIS AND PROGRAMMING DETAILS

11.1.1 Analysis of Covariance

This test will be used for testing whether population means of response variable (e.g. change in HbA1c from baseline to week 24) are equal across levels of treatment (MP-513 and Placebo) after controlling for the effect of continuous covariate i.e. baseline value and fixed effects i.e. treatment. Following code can be used for fitting ANCOVA model:

```
proc mixed data=mydata(where=(visit='Week 24'));  
  class trt;  
  model change = base trt/solution ddfm=kr;  
  lsmeans trt/diff=CONTROL('placebo') cl;  
  Ods output LSMeans = lsm (keep=trt estimate);  
  Ods output Diffs = diff1sm;  
run;
```

Where,

- Response variable 'change' is the change from baseline to an endpoint visit
- trt is a categorical variable for treatment group (MP-513 or placebo)
- base is continuous baseline covariate
- Class statement specifies the classification variables.

- *diff=CONTROL* requests the differences with a control that, by default, is the first level of the specified LS-mean effect. Thus to specify which level is to be considered as control specify that in parentheses i.e. ('placebo'),
- Dataset '*lsm*' will contain the estimate for least square means (LS-means) for treatment groups under the variable 'estimate'.
- Dataset '*diff_lsm*' will contain estimate of difference of LS- means under variable 'estimate', standard error of LS -means difference under variable 'stderr', p value (using t test) for testing the significance of the difference between LS-means under variable 'probt' and the confidence limits for difference of LS-means under variable 'lower' and 'upper'.

11.1.2 Mixed Effects Model for Repeated Measure Analysis

This test will be used for testing whether population means of response variable (e.g. change in HbA1c from baseline to week 24) are equal across levels of treatment (MP-513 and Placebo) after controlling for the effect of continuous covariate i.e. baseline value and fixed effects i.e. treatment, visit and interaction of treatment and visit. Following code can be used for MMRM analysis:

```
proc mixed data=mydata;
  class subid trt visit;
  model change = base trt visit trt*visit / solution ddfm=kr;
  repeated visit/ subject=subid type=un;
  lsmeans trt*visit/cl diff;
  ods output LSMeans = lsm(keep=trt visit estimate where=(trt='MP-513' and
    visit='Week 24'));
  ods output Diffs = diff_lsm(keep=trt visit _trt _visit estimate stderr
    probt lower upper where=(trt='MP-513' & _trt='Placebo'
    & visit='Week 24' & _visit='Week 24'));
```

run;

Where,

- Response variable 'change' is the change from baseline to different visits.
- Class statement specifies the classification variables.
- trt is a categorical variable for treatment group (MP-513 or placebo)
- base is continuous baseline covariate
- Ddfm=kr specifies 'Kenwardroger' method of computing denominator degree of freedom for the tests of fixed effects.
- Type= un specifies the within- subject variance covariance matrix as 'unstructured variance covariance matrix'.
- Dataset '*lsm*' will contain the estimate for least square means (LS-means) for treatment groups at week 24 under the variable 'estimate'.
- Dataset '*diff_lsm*' will contain estimate of difference of LS- means under variable 'estimate', standard error of LS-means difference under variable 'stderr', p value (using t test) for testing the significance of the difference between LS-means under variable 'probt' and the confidence limits for difference of LS-means under variables 'lower' and 'upper'.

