1.2. Protocol Synopsis

Sponsor: Mitsubishi Tanabe Pharma Corporation	Name of Medical Product: MP-513	Active Ingredient(s): Teneligliptin
Study Centre(s): Multi-centre study that will be conducted in approximately 35 sites in China		
Study Duration: 30 weeks (2 weeks screening, 2 weeks placebo run-in, 24 weeks treatment, 2 weeks follow-up) The study period is estimated to start from [REDACTED] to [REDACTED].		Study Phase: 3
Study Title: A phase 3 randomized, double-blind, placebo-controlled parallel group efficacy and safety monotherapy study of MP-513 in Chinese subjects with type 2 diabetes mellitus inadequately controlled with diet and exercise		
Study objectives: To evaluate the efficacy and safety of MP-513 compared with placebo in Chinese subjects with type 2 diabetes mellitus inadequately controlled with diet and exercise		
Methodology: Multi-centre, randomized, double-blind, placebo-controlled, parallel-group study		
Number of Subjects (Planned): 240 subjects (120 subjects to MP-513 and 120 subjects to placebo)		
Diagnosis and Inclusion Criteria: The subjects have to meet all of the following inclusion criteria: 
 1. A signed and dated informed consent form has been obtained from the subject, in accordance with International Conference on Harmonisation guidelines on Good Clinical Practice (ICH GCP), before any screening or study related procedures take place. 2. The subject is aged ≥ 18 years at signature of the informed consent form 3. Hospitalization status: outpatient 4. The subject has had a documented diagnosis of type 2 diabetes mellitus for at least 3 months at the screening visit (Day -28) 5. The subject is undergoing diet and exercise therapy, and diet and exercise regimen has not been changed for at least 8 consecutive weeks at the screening visit (Day -28). Subjects who cannot do exercise due to complication are not limited to this criteria. 6. The subject's glycosylated fraction of haemoglobin (HbA1c) is $\geq 7.0\%$ and $< 10.0\%$ at the screening visit (Day -28) and on Day -14. 7. The subject's fasting plasma glucose (FPG) is < 270 mg/dL (15 mmol/L) at the screening visit (Day -28) and on Day -14. 8. The subject is capable of giving informed consent, complying with the restrictions and requirements of the protocol and, in the opinion of the investigator, will be able to complete the study. 		

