6.4.2 Method of Assigning Subjects to Treatment Groups

Subjects will be randomized to MP-513 or placebo in a 1:1 ratio according to a computer-generated randomization code.

Treatment assignment will be managed through static blocked randomization and an Interactive Web Randomization System (IWRS) will be used.

The randomization scheme will be reproducible and will be prepared by the CRO via a computerized system prior to start of the study. Separate lists will be prepared for subjects' randomization (randomization code list) and study medication packaging (kit code list).

The IWRS provider will retain master copies of the randomization and kit code list (in a secure fashion in order to maintain the blind).

At the randomization visit (Day 1), after confirmation of subject eligibility, the Investigator will connect to the randomization system in order to receive kit number containing the study treatment, then subjects will receive the double-blinded study treatment which is assigned to them.

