6.9.1.1 General Considerations

All significance tests will be carried out at a 5%, 2-sided significance level. Statistical tests will be supported by presenting estimates and 95% confidence intervals for the respective treatment effects and differences between the treatment groups. These estimates, confidence intervals and p-value will be based on the respective statistical models used for the analysis.

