6.9.1.5 Efficacy Parameters

(1) Primary efficacy endpoint

The primary efficacy endpoint is the change in HbA1c from baseline to Week 24.

Primary analysis: The change in HbA1c from baseline to Week 24 between treatment groups will be analysed using analysis of covariance (ANCOVA), with treatment as fixed effect and baseline value as a covariate. Missing values at Week 24 will be imputed using LOCF approach. Primary analysis on primary efficacy endpoint will be presented for FAS.

Supportive analysis:

The same statistical methodology as described for primary analysis will be performed for PPS.

The change in HbA1c from baseline to Week 24 between treatment groups will be analysed using mixed-effects model for repeated measures, with treatment, visit and interaction of treatment and visit as fixed effects and baseline value as a covariate. An unstructured covariance matrix will be used to model the covariance of within-patient scores. No imputation will be implemented for missing values. This analysis will be presented for FAS.

(2) Secondary efficacy endpoint

The secondary efficacy endpoints are the change in FPG from baseline to Week 24.

The same statistical methodology as described for primary analysis on primary efficacy endpoint will be used. Analyses on secondary efficacy endpoint will be presented for FAS.

(3) Other efficacy endpoints

The other efficacy endpoints are;

- Proportion of subjects who achieved HbA1c < 7.0% at Week 24
- Change in fasting insulin, C-peptide, and glucagon from baseline to Week 24
- Change in HOMA-IR and HOMA-β from baseline to Week 24
- Change in body weight from baseline to Week 24
- Change in body weight from baseline to Week 12

For the proportion of subjects who achieved HbA1c < 7.0% at Week 24, the comparison between treatments will be performed using logistic regression with treatment as fixed effect and baseline value as a covariate. The subjects who has HbA1c ≤ 7.0% at baseline will be excluded from the analysis.

For the others, the same statistical methodology as described for primary analysis on primary efficacy endpoint will be used. Analyses on other efficacy endpoint will be presented for FAS.

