8.7.1.2 Supportive Analysis of Primary Efficacy Variable

The study will have two supportive analyses to be performed on primary efficacy variable i.e. change in HbA1c from baseline to Week 24, as follows:

- The change in HbA1c from baseline to Week 24 in MP-513 compared to Placebo will be performed on PPS using the same statistical methodology as described for the primary analysis.

The change in HbA1c from baseline to Week 24 in MP-513 compared to Placebo will be analysed using mixed effects model for repeated measure (MMRM), with treatment, visit and interaction of treatment and visit as fixed effects and baseline value as a covariate in the model. An unstructured covariance matrix will be used to model the covariance of within-subject values. The Kenward-Roger approximation will be used to estimate denominator degrees of freedom (Kenward and Roger, 1997). For this analysis, missing data will not be imputed, i.e. only the observed data will be used.

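### The supportive MMRM fits one baseline slope for all six visits; if the slope changes over time, the Week 24 estimate loses some precision and can shift slightly towards MP-513

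*SAP*

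**What the plan says.** Protocol 6.9.1.5 specifies a supportive repeated-measures model "with treatment, visit and interaction of treatment and visit as fixed effects and baseline value as a covariate". SAP 8.7.1.2 repeats this: "with treatment, visit and interaction of treatment and visit as fixed effects and baseline value as a covariate in the model". The code in SAP 11.1.2 agrees: "model change = base trt visit trt*visit / solution ddfm=kr", with an unstructured within-subject covariance, "repeated visit/ subject=subid type=un". The synopsis lists the same fixed effects. No baseline-by-visit term appears anywhere, so the sources are consistent with each other.

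On missing data, SAP 8.7.1.2 states: "For this analysis, missing data will not be imputed, i.e. only the observed data will be used". The primary analysis (SAP 8.7.1.1) is a single-visit ANCOVA on Week 24 with LOCF, which fits its own Week 24 baseline slope. The other supportive analysis repeats that ANCOVA, LOCF included, in the per-protocol set.

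**The concern.** The treatment effect is allowed to differ by visit, but the baseline effect is not. SAP 4.2 describes HbA1c as settling over the 24 weeks, so change is probably still developing at Weeks 4 and 8. Change at Week 24 may then depend on baseline more strongly than change at Week 4. A common slope is weighted towards the early visits, where residual variation is likely to be smaller, and would be too shallow at Week 24.

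There are three possible consequences.

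- Part of the Week 24 variation that baseline could explain stays in the residual, so the standard error grows. This needs no dropout.
- Protocol 6.3.3 discontinues subjects whose FPG exceeds limits that tighten over time, so dropout is tied to glycaemia. The wrong slope then enters what the model implies for missing visits. If more placebo subjects leave, and those with higher baselines leave more often, a slope that is too shallow makes the placebo mean look worse at Week 24.
- A gap between the MMRM and the primary ANCOVA would mix two causes: different handling of missing data and different baseline adjustment. Only the first is what the check is meant to show.

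**Working it through.** **Inputs from the documents.** Planned size is "240 subjects (120 subjects to MP-513 and 120 subjects to placebo"), allocated 1:1, with two-sided 5% tests and six post-baseline visits. Eligibility HbA1c is 7.0% to below 10.0%. FPG discontinuation limits are above 270, 240 and 200 mg/dL in successive periods (Protocol 6.3.3). Earlier results in Protocol section 4 give scale: a placebo-subtracted effect of -0.48 at Week 24 (20 mg with metformin), one of -0.79 at Week 12 (monotherapy), and an SD of change of 0.67 at Week 52 (monotherapy). The sample-size section is redacted, so there is no planned figure to reproduce.

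**Assumptions, none given in the documents.** Baseline is truncated normal on 7–10%. The Week 24 effect is -0.60. Residual SD rises from 0.4 to 0.7. Correlation between visits is 0.85 to the power of the lag. FPG is tied linearly to HbA1c with noise and drives dropout through the Protocol 6.3.3 limits, with 1% random loss per visit. This gives dropout of about 16% placebo / 9% active (lighter) or 29% / 16% (heavier). Four slope patterns from Week 4 to Week 24 were used.

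**Step 1: precision, by formula.** With complete data, the Week 24 difference is the difference in mean change minus the fitted slope times the difference in mean baseline. Its variance is inflated by

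1 + g² × Var(baseline) / σ²,

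where g is the gap between the true Week 24 slope and the common slope, and σ = 0.7. With a baseline SD of 0.7 the factor is simply 1 + g²:

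- mild, g ≈ 0.15: √1.0225 = 1.011
- moderate, g ≈ 0.30: √1.09 = 1.044
- strong, g ≈ 0.43: √1.185 = 1.089

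The baseline SD matters. For g = 0.25, SD 0.65 gives 0.0625 × 0.4225 / 0.49 = 5.4% in variance (2.7% in SE), and SD 0.8 gives 0.0625 × 0.64 / 0.49 = 8.2% (4.0% in SE). For g = 0.43, the SE increase is 7.7% at SD 0.65 and 11.4% at SD 0.8.

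**Step 2: simulation.** Unstructured models with and without the interaction were fitted to the same data. Large-sample runs used 60,000 subjects. Trial-size runs used 240 subjects; the varying-slope patterns had 400–500 replicates each.

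| Slope pattern, Week 4 to 24 | Fitted common slope | SE ratio, large sample | Rise in empirical SD, N=240 | Shift, large sample | Mean shift, N=240 |
|---|---|---|---|---|---|
| Flat, -0.30 | -0.30 | 1.00 | none | 0.0001 or less | -0.0003 (lighter dropout only) |
| Mild, -0.15 to -0.30 | about -0.15 | 1.01 | 0% | -0.002 to -0.003 | -0.003 to -0.005 |
| Moderate, -0.10 to -0.40 | about -0.10 | 1.04–1.05 | 2–3% | -0.004 to -0.008 | -0.007 to -0.011 |
| Strong, -0.05 to -0.50 | about -0.065 | 1.09 | 6–7% | -0.007 to -0.014 | -0.010 to -0.017 |

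Shift means common-slope estimate minus interaction estimate; negative favours MP-513. The simulated SE ratios agree with Step 1.

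**Step 3: does the shift need dropout?** Without dropout, the mean shift at N=240 is -0.001 to -0.002. The Monte Carlo error is of similar size (moderate: 0.028 / √400 = 0.0014). The bias therefore comes from dropout. The SE is still larger without dropout: 0.094 against 0.091 (moderate) and 0.098 against 0.091 (strong).

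**Step 4: scale.** The largest shift, 0.017, is 0.017 / 0.60 = 2.8% of the assumed effect and 0.017 / 0.48 = 3.5% of the earlier Week 24 effect. It is 0.017 / 0.096 = 0.18 of a standard error. With the interaction, the N=240 mean is about -0.603 against a true -0.600 in all three varying patterns.

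**The case against.** The model as written is a legitimate, pre-specified MMRM, and protocol, SAP text and code agree. The harm is conditional: with flat slopes there is none, and with mild variation the empirical SD does not change. Flat or mild slopes cannot be excluded. Change scores share measurement error with baseline, so part of the negative slope is present at the first visit and needs no time to develop. The analysis is supportive, and the shift is a fraction of a standard error. As context, 120 per arm gives 96% power for a difference of 0.48 even at an SD of 1.0. All of this stands.

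A reader might infer three stronger things that the documents do not support.

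- That the supportive analysis is materially biased. This would need known visit-specific slopes and heavy, unequal dropout; the documents give neither.
- That the MMRM is the only look at Week 24 without imputation. SAP 8.7.1.1 also plans descriptive summaries at every post-baseline visit and a graph showing observed Week 24 and Week 24 (LOCF) separately with 95% intervals. The MMRM is the only non-imputing inferential model.
- That the extra term repairs the effect of the withdrawal rule. That rule acts on FPG, which is not in the model.

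What the objection does not remove is that the richer model costs almost nothing if slopes are flat and is better if they are not.

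**Conclusion.** The point holds as a free improvement, not as an error in the plan. If baseline slopes differ across visits, the common slope is pulled to the early-visit value. The Week 24 SE is then larger by about 1% (mild), 2–5% (moderate) or up to about 10% (strong), and by nothing if slopes are flat. With glycaemia-related dropout heavier on placebo, the estimate shifts by 0 to about 0.017 HbA1c points. The shift favours MP-513, so it is not conservative.

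Slopes, baseline SD, residual SD, correlation and dropout rates are all assumptions, and the size should be read only as a range. The primary ANCOVA is unaffected and the trial's conclusion is unlikely to change. The main gain is interpretive. With a baseline-by-visit term, unstructured covariance and complete data, the MMRM's Week 24 difference equals that of a Week 24 ANCOVA, so a gap from the primary result would reflect missing-data handling.

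**What to change.** Before unblinding:

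- Insert `base*visit` after `trt*visit` in the MODEL statement of SAP 11.1.2.
- Add the baseline-by-visit interaction to the fixed effects in SAP 8.7.1.2.
- Record it in SAP section 5, which now states that no changes are planned, as a change from Protocol 6.9.1.5.

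The cost is one model term: six baseline slopes instead of one, so five more parameters with 240 planned subjects. The primary analysis and data collection stay as they are. The report should not present the term as a remedy for dropout that depends on unobserved values or on FPG beyond HbA1c.
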